6.4.2 EXAMINATION OF THE INJECTION SITE

At all visits the physical examination will include a careful examination of the injection site including measurements of the circumference of the extremity where appropriate if there is clinical evidence of a local reaction. Patients will be monitored throughout the study period for anti-DNA antibodies, rheumatoid factors and evidence of muscle destruction. Levels of anti-DNA antibodies and rheumatoid factors will be measured according to standard local ranges. If these tests should become significantly positive, after previously being absent or normal or other clinically significant signs of autoimmunity appear, vaccination will be terminated and rheumatology consultation will be sought.

6.4.3 ASSESSMENT OF PAIN AFTER INJECTION

Acute pain immediately after injection and delayed pain will be assessed by questionnaire for all patients (see Appendix 1 and 2).

6.4.4 ACCIDENTAL SPILLAGES

Accidental spillages should be dealt with according to hospital policy. The product is non-toxic and non-infectious. Spillage will be treated with 1000ppm hypochloride solution. It can then be wiped up and the tissue disposed of in autoclavable bags/containers. Syringes will be disposed of in autoclavable containers.

6.5 DRUG ACCOUNTABILITY

Accurate records of all drug shipments, vaccine dispensed, and all vaccine returned must be maintained. This inventory record must be available for inspection by UHS or the UoSCTU at any time. Drug supplies are to be used only in accordance with this protocol and under the supervision of the Investigator.

Empty vials of vaccine will be shipped back to, the Quality Assurance Manager, [name] by first class post using appropriate packaging. Alternatively they will be collected by a member of the UoSCTU staff at a scheduled monitoring visit.

The Investigator undertakes not to destroy any unused drug unless directed to by UHS or the UoSCTU. Any destroyed study drug must be destroyed according to hospital procedures and properly accounted for. At the conclusion of the study the overall numbers of the drug shipped to the centre, and the number destroyed or returned will be provided by the pharmacy, and an account given of any discrepancy. Any vaccine remaining will be returned to the Chief Investigator.

7 ASSESSMENT OF SAFETY

The recent reporting of trials using DNA vaccination in normal volunteers and in HIV infected individuals confirms our own findings that the procedure is safe and extends the safe dose range up to $2,500\mu$ g. Thus, although the potential toxicities are discussed below and will be looked for, the procedure appears very safe.

7.1 SAFETY CONSIDERATIONS OF DNA VACCINATION +/- ELECTROPORATION

7.1.1 SAFETY OF THE ELGEN PULSE GENERATOR AND THE TWIN INJECTOR

The Elgen pulse generator and a syringe based electrode system has been tested and approved according to Electromagnetic Compatibility (EN 60601-1-2:1993, EN 61000-3-2:2000, EN 61000-3-3:1995 + A1:2001). It has also been tested according to: IEC 60601-2-10, 1st ed. 1987 + A1: 2001, EN 60601-1-10:2000+A1:2001, Medical equipment, part 2: Particular requirements for the safety of nerve muscle stimulators. (The system failed to pass the limitations requirements for output parameters for nerve muscle stimulators, this is because the currents and voltages needed to perform EP is larger than what is necessary to perform standard nerve-muscle stimulation).

7.1.2 LOCAL TOXICITY AT THE INJECTION SITE

There exists the possibility of pain, tenderness and inflammation at the site of intramuscular injection of the DNA construct, caused by the DNA itself, impurities in the DNA, or by the protein encoded by the DNA construct. Additionally electroporation has so far only been tested in a cohort of healthy volunteers and in 32 patients with prostate cancer. While no local toxicity of grade WHO >2 has been found, careful monitoring of the injection site is therefore crucial:

- Assessment of local toxicity will be according to CTC criteria.
- Any visible local injection sites will be documented electronically by digital photography
- CK and anti-skeletal muscle antibodies will be measured to assess auto-immune muscle damage. If there is evidence of muscle damage myoglobin will be measured using local standards.
- Persistent or rising levels of CK or anti-skeletal muscle antibodies will be taken to indicate muscle damage.

This is unlikely based on animal experiment but if it occurs the vaccination will be stopped and full rheumatological assessment will be arranged.

7.1.3 ASSESSMENT OF PAIN AND DISCOMFORT POST INJECTION

For all patients pain or discomfort and level of distress will be assessed 1 hr after injection (or after recovery from sedation) and at 48 hrs. The information will be collected, using a questionnaire (see Appendix 1 & 2).

7.1.4 PAIN MANAGEMENT AFTER VACCINATION:

The following are suggested for pain control after evaluation of the pain using the pain evaluation tools in Appendix 1 & 2:

Mild pain/discomfort - 1-4	No intervention
Moderate pain - 5-6	Paracetamol 1 g qds
Severe Pain - 7-10	Co-codamol 30/500 2 tabs qds +/- Ibuprofen 400 mg qds

Patients will be offered paracetamol to take home and will be reviewed early if severe pain occurs.

7.1.5 IMMEDIATE HYPERSENSITIVITY

Immediate hypersensitivity to injected DNA has not previously been observed. Nevertheless, the possibility of anaphylactic, febrile or other systemic reactions exists, either to the DNA itself or to impurities present in the vaccine preparation.

• Vital signs will be monitored closely after administration of the DNA. If anaphylaxis occurs, the patient should be treated immediately, initially with adrenaline, hydrocortisone and chlorpheniramine.

7.1.6 ANTI-DNA ANTIBODIES

Anti-nuclear and anti-DNA antibodies are characteristic of systemic lupus erythematosus (SLE), an autoimmune disease with diverse clinical manifestations. It is not clear whether the anti-DNA antibodies are important in the pathogenesis of this disorder, although the antibody titre does carry prognostic significance. It is conceivable that repeated inoculations with unmodified plasmid DNA could give rise to anti-DNA antibody responses leading to the development of an SLE-like syndrome. However, experimental evidence from animal and our own human studies with ca 100 patients and close to 1000 DNA vaccine applications suggests that this is a very unlikely possibility.

- Anti DNA antibodies will be measured sequentially.
- In the unlikely event that such antibodies should appear, the treatment will be stopped and the rheumatologists will be consulted.

7.1.7 GERM LINE GENE TRANSFER

Gene integration is expected to take place after IM injections at a very low frequency. When EP is applied the probability of integration will increase. Since the amount of DNA entering each cell is likely to increase between 100-1000 fold, a corresponding increase in integration probability will take place. In addition we do not know to which extent the electrical currents will influence the structure of the plasmid or nuclear DNA and if that could increase the integration rate. If there is an enhanced probability of integration, this is likely to be effective only at site of injection and these cells will be eliminated as a result of the immune response.

Plasmid DNA administered by the intramuscular route may gain access to the blood circulation through the walls of small blood vessels in the vicinity of the inoculum. Damage to these blood vessels may occur at the time of DNA inoculation. There is therefore a theoretical possibility that circulating plasmid DNA could localise in gonadal tissues, enter the nuclei and integrate into the chromosomes of germ cells or their precursors. Such genetic modification of germ line cells is undesirable and intentional modification of the human germ line is not permitted in any country.

• Any sexually active and fertile patients will be instructed to use appropriate contraceptive measures in line with the advice given to patients undergoing treatment for potentially mutagenic drugs (eg. cytotoxic chemotherapy). They will be asked to take such precautions at study entry, during the period of vaccination and for six months afterwards.

7.1.8 OTHER SYSTEMIC TOXICITY

Haematological toxicity: It is possible that vaccination with WT1 may cause cytopaenias in patients who have a hypocellular low marrow reserve (hypocellular bone marrow). This is because WT1 is also expressed at low levels in normal CD34+ stem cells. To minimise the possibility of this, we will exclude patients with low marrow reserve (bone marrow cellularity <20%). Patients who develop cytopaenia will be treated with 5 days of intravenous methylprednisone (1-2 mg/kg). This steroid treatment will not start for 2-3 weeks after the start of cytopaenia to allow time to determine if cell counts rebound. They will also be given supportive care including blood products, growth factors and antibiotics as clinically indicated until the counts recover. The development of other systemic toxicity appears unlikely. FBC, biochemistry, in particular renal function and clinical AE will be assessed by CTC criteria.

• If CTC toxicity >2 occurs in a particular patient, vaccination will be paused. Further vaccination may be offered after normalization if appropriate in the opinion of the treating clinician and only after documented discussion with the UoSCTU and lead investigators.

Cardiac or renal toxicity: It is possible but from the available dataset in the literature unlikely, that the patients may develop immune related toxicity that affects the kidney or cardiac function. Patients will therefore have regular monitoring of their renal function, including urine sampling for proteinuria, and an ECG before any vaccination dose is given. Additional tests will be undertaken as clinically indicated, should signs of renal or cardiac dysfunction occur.

8 PHARMACOVIGILANCE

8.1 **DEFINITIONS**

The Medicines for Human Use (Clinical Trials) Regulations 2004, as amended, provides the following definitions relating to adverse events in trials with an investigational medicinal product:

Adverse Event (AE): any untoward medical occurrence in a patient or clinical trial subject administered a medicinal product and which does not necessarily have a causal relationship with this treatment. *An AE can therefore be any unfavourable and unintended sign (including an abnormal laboratory finding), symptom, or disease temporally associated with the use of an investigational medicinal product (IMP), whether or not considered related to the IMP.*

Adverse Reaction (AR): all untoward and unintended responses to an IMP related to any dose administered.

All AEs judged by either the reporting investigator or the sponsor as having reasonable causal relationship to a medicinal product qualify as adverse reactions. The expression reasonable causal relationship means to convey in general that there is evidence or argument to suggest a causal relationship.

Unexpected Adverse Reaction: an AR, the nature or severity of which is not consistent with the applicable product information (e.g. investigator's brochure (IB) for an unapproved investigational product).

When the outcome of the adverse reaction is not consistent with the applicable product information this adverse reaction should be considered as unexpected. Side effects documented in the IB which occur in a more severe form than anticipated are also considered to be unexpected.

Serious Adverse Event (SAE) or Serious Adverse Reaction (SAR): any untoward medical occurrence or effect that at any dose:

- Results in death
- Is life-threatening refers to an event in which the subject was at risk of death at the time of the event; it does not refer to an event which hypothetically might have caused death if it were more severe
- Requires hospitalisation, or prolongation of existing inpatients' hospitalisation
- Results in persistent or significant disability or incapacity
- Is a congenital anomaly or birth defect

Medical judgement should be exercised in deciding whether an AE/AR is serious in other situations. Important AE/ARs that are not immediately life-threatening or do not result in death or hospitalisation but may jeopardise the subject or may require intervention to prevent one of the other outcomes listed in the definition above, should also be considered serious.

Suspected Unexpected Serious Adverse Reaction (SUSAR): any suspected adverse reaction related to an IMP that is both unexpected and serious.
8.2 CAUSALITY

Most adverse events and adverse drug reactions that occur in this trial, whether they are serious or not, will be expected treatment-related toxicities due to the drugs used in this trial. The assignment of the causality should be made by the investigator responsible for the care of the subject using the definitions in the table below.

If any doubt about the causality exists the local investigator should inform the University of Southampton Clinical Trials Unit (UoSCTU) who will notify the Chief Investigator. Pharmaceutical companies and/or other clinicians may be asked for advice in these cases.

In the case of discrepant views on causality between the investigator and others, all parties will discuss the case. In the event that no agreement is made, the MHRA will be informed of both points of view.

Relationship	Description
Unrelated	There is no evidence of any causal relationship
Unlikely	There is little evidence to suggest there is a causal relationship (e.g. the event did not occur within a reasonable time after administration of the trial medication). There is another reasonable explanation for the event (e.g. the subject's clinical condition, other concomitant treatment).
Possible	There is some evidence to suggest a causal relationship (e.g. because the event occurs within a reasonable time after administration of the trial medication). However, the influence of other factors may have contributed to the event (e.g. the subject's clinical condition, other concomitant treatments).
Probable	There is evidence to suggest a causal relationship and the influence of other factors is unlikely.
Definitely	There is clear evidence to suggest a causal relationship and other possible contributing factors can be ruled out.

8.3 **REPORTING PROCEDURES**

All adverse events should be reported. Depending on the nature of the event the reporting procedures below should be followed. Any questions concerning adverse event reporting should be directed to the UoSCTU in the first instance. A flowchart will be provided to aid in the reporting procedures.

8.3.1 PRE-EXISTING CONDITIONS

A pre-existing condition should not be reported as an AE unless the condition worsens by at least one CTCAE grade during the trial. The condition, however, must be reported in the pre-treatment section of the CRF, if symptomatic at the time of entry, or under concurrent medical conditions if asymptomatic.

8.3.2 NON SERIOUS AR/AES

All such toxicities, whether expected or not, should be recorded in the toxicity section of the relevant case report form and sent to the UoSCTU within one month of the form being due.

8.3.3 SERIOUS ADVERSE EVENTS AND REACTIONS

Fatal or life threatening SAEs and SUSARs should be reported within 24 hours of the local site becoming aware of the event. The SAE/SUSAR form asks for nature of event, date of onset, severity, corrective therapies given, outcome and causality (i.e. unrelated, unlikely, possible, probably, definitely). The responsible investigator should assign the causality and expectedness of the event with reference to the current IMP IB and use the event terms and grades given in the NCI CTCAE v4.0. Additional information should be provided as soon as possible if the event/reaction has not resolved at the time of reporting.

Relapse and death due to CML or AML, and hospitalisations for elective treatment of a pre-existing condition do not need reporting as SAEs.

8.3.4 REPORTING DETAILS

An SAE/SUSAR form should be completed for all SAEs and SUSARS and faxed to the UoSCTU within 24 hours.

Complete the SAE/SUSAR form & fax or email a scanned copy of the form with as many details as possible to the UoSCTU together with anonymised relevant treatment forms and investigation reports.

Or

Contact the UoSCTU by phone for advice and then fax or email a scanned copy of the completed SAE/SUSAR form.

The UoSCTU will notify the necessary competent authorities and main REC of all SUSARs occurring during the trial according to the following timelines; fatal and life-threatening within 7 days of notification and non-life threatening within 15 days. All investigators will be informed of all SUSARs occurring throughout the trial.

Local investigators should report any SUSARs and /or SAEs as required by their Local Research Ethics Committee and/or Research & Development Office.

8.3.5 FOLLOW UP AND POST-STUDY SAES

The reporting requirement for SAEs affecting subjects applies for all events occurring up to 4 weeks after the last administration of study drugs. All unresolved adverse events should be followed by the investigator until resolved, the subject is lost to follow-up, or the adverse event is otherwise explained. At the last scheduled visit, the investigator should instruct each subject to report any subsequent event(s) that the subject, or the subject's general practitioner, believes might reasonably be related to participation in this study. The investigator should notify the study sponsor of any death or adverse event occurring at any time after a subject has discontinued or terminated study participation that may reasonably be related to this study.

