5.2 VACCINE SCHEDULE

The DNA vaccine will be administered 6 times every 4 weeks followed by a further 6 vaccinations every 3 months to maximum of 24 months.

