9 ASSESSMENT AND FOLLOW-UP OF PATIENTS

It is intended that all patients will be followed on study for up to 36 months from date of informed consent. Date and type of subsequent treatments and survival data for all patients will be collected prospectively.

9.1 **PRE-TREATMENT EVALUATIONS**

The following investigations should be performed within 1 month of starting treatment. (It is anticipated that these investigations will be performed as standard clinical care; if they are not, consent must be obtained prior to any study related procedure/s):

- Bone Marrow aspirate for assessment of bone marrow cellularity and immunological evaluation (all patients except HLA A2 negative CML patients) and for disease evaluation (in AML) If a bone marrow sample is available within 1 month prior to recruitment in the study, a second bone marrow examination is not performed, unless clinically indicated.
- Chest X-Ray (HLA A2 positive patients only)
- ECG (HLA A2 positive patients only)
- Echocardiogram (HLA A2 positive patients only)

The following investigations/evaluations should be performed after consent and registration, and prior to starting treatment:

- HLA Status
- Demographic data
- Medical history
- Prior treatment malignancy
- Height and weight
- Physical examination
- WHO Performance status
- Vital Signs
- FBC and differential blood count, ESR
- Clotting
- Biochemistry
- CK test (HLA A2 positive patients only)
- Urine analysis (HLA A2 positive patients only)
- Syphilis, Hep B, Hep C, HIV
- Blood for immunological assays (80 ml of anticoagulated blood)
- qPCR for BCR-ABL and WT1 in CML, for WT1 in AML
- Leukapheresis for immunological studies (HLA A2 positive patients only)

- Autoimmune profile
- Concomitant diseases/treatments
- Adverse Events

Please also refer to the tabulated Schedule of Observations and Procedures (on pages 13-16).

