9.3 EVALUATIONS DURING AND AT THE END OF THE STUDY

HLA Status: Registratio	n
Visit 0: Baseline (once	
Visit 1: week 0	within 7 days of baseline visit
Visit 2: week 2	14 days after v1 +/- 3 days (Not done for HLA A2 negative patients)
Visit 3: week 4	14 days after v2 +/- 7 days
Visit 4: week 8	28 days after v3 +/- 7 days
Visit 5: week 10	14 days after v4 +/- 3 days (Not done for HLA A2 negative patients)
Visit 6: week 12	14 days after v5 +/- 7 days
Visit 7: week 16	28 days after v6 +/- 7 days
Visit 8: week 20	28 days after v7 +/- 7 days
Visit 9: week 22	14 days after v8 +/- 3 days
Visit 10: week 24-28	14-42 days after v9 +/- 14 days
Visit 11: week 32	56-28 days after v10 (depending on date of v10) +/- 14 days
Visit 12: week 34	14 days after v11 +/- 3 days
Visit 13:	11 months after baseline +/- 14 days
Visit 14:	14 months after baseline +/- 14 days
Visit 15:	17 months after baseline +/- 14 days
Visit 16:	14 days after visit 15 +/- 3 days
Visit 17:	20 months after baseline +/- 14 days
Visit 18:	23 months after baseline +/- 14 days
Visit 19:	24 months after baseline +/- 14 days
Visit 20:	27 months after baseline +/- 14 days
Visit 21:	30 months after baseline +/- 14 days
Visit 22:	33 months after baseline +/- 14 days
Visit 23:	36 months after baseline +/- 14 days
After Visit 23, month 3	6, follow-up outcomes should continue to be recorded.

If delays occur on vaccination visits, all subsequent visits will be slipped to keep the interval between vaccinations at 1 and 3 months, respectively. The day 14 post vaccination visits (v2, v5, v9 and v12) should be kept as close to 14 days as possible, allowed +/- 3 days.

Investigations required at each visit:

- FBC and differential blood count, ESR
- Biochemistry
- CK test (HLA A2 positive patients only)
- Urine analysis (HLA A2 positive patients only)

- Immunological monitoring*; 65 ml of anticoagulated blood (Lithium Heparin Tubes) and 5 mL clotted blood for serum will be taken for this purpose. (Blood should be taken prior to vaccine being administered).

Investigations required at visits 1, 2, 3, 4, 6, 7, 8, 11, 13, 14, 15, 17 and 18:

- Height and weight
- Physical examination
- WHO performance status
- Vital signs

HLA A2 positive patients only - Additional investigations required after each vaccination*(Visits 1, 3, 4, 6, 7, 8, 11, 13, 14, 15, 17 and 18):

- ECG
- Echocardiogram (if clinically indicated)
- Assessment of pain and discomfort of vaccination sites

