10.2 ANALYSIS PLAN

Molecular Analysis

The analyses on molecular response will be performed on all patients with molecular data at a minimum of 2 post-baseline time points (HLA A2 positive patients must also have received at least 1 dose of the vaccine).

Immunological Analysis

To be evaluable for immunological response, positive HLA A2 patients must receive at least 1 dose of the vaccine and the immunological testing must be available until at least week 8 post first dose.

Safety Analysis

For safety analyses, all patients with positive HLA A2 status who received at least one study drug administration will be evaluable for toxicity. All controls will be included in the safety analyses, where relevant.

Other Analysis

For all other analyses, an intention to treat principle will be used.

10.2.1 ANALYSIS FOR CML PATIENTS ONLY:

Primary:

The primary endpoint is molecular response of BCR-ABL (major or minor response or CMR). For the purpose of analysis, response (as defined by section 9.6) will be measured at weeks 4, 8, 12, 16, 20, 32 and 11, 17 and 23 months. Fisher's exact test will be used to compare differences in proportions of molecular response in CML patients versus controls.

Secondary:

The primary analysis will be repeated for major response or CMR of BCR-ABL.

The analysis methods used for BCR-ABL will be repeated for WT1.

Progression free survival, duration of response and overall survival (as defined in Section 2.2) will be estimated using the method of Kaplan and Meier for each group. Survival estimates will be presented with 90% confidence intervals. These endpoints will also be compared between the CML patients and controls using log-rank tests.

Progression free survival for CML patients is defined in Section 2.2 and is measured as the time from date of consent to the study to date of progression or death from any cause. Alive patients who are progression free will be censored at their date of last follow up. Similar analysis will be performed for overall survival and duration of response.

Toxicity will be collected and evaluated according to the NCI CTC toxicity scale (v4.0) and compared between the vaccinated and control groups by Fisher's exact test.

10.2.2 ANALYSIS FOR AML PATIENTS ONLY:

Primary:

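### SAE reporting closes four weeks after the last dose, leaving later on-study events without a clear expedited route and controls without any window; separately, the between-group toxicity test rests on unequal ascertainment

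*Protocol*

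**What the plan says.** **SAE window.** Section 8.3.5 sets the rule: "The reporting requirement for SAEs affecting subjects applies for all events occurring up to 4 weeks after the last administration of study drugs". The same section asks the investigator to notify the sponsor of "any death or adverse event occurring at any time after a subject has discontinued or terminated study participation", provided the event may reasonably be related to the study. It also requires unresolved adverse events to be followed.

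**Follow-up and dosing.** Section 9: "It is intended that all patients will be followed on study for up to 36 months from date of informed consent". Section 5.2: "The DNA vaccine will be administered 6 times every 4 weeks followed by a further 6 vaccinations every 3 months to maximum of 24 months". In Section 9.3 the last vaccination visit is visit 18, at month 23. Section 4.4 lists reasons for stopping vaccination early, including toxicity and disease progression. Under Section 5, HLA A2 negative patients receive standard care and no vaccine.

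**Safety analysis.** Section 10.2: "All controls will be included in the safety analyses, where relevant". Sections 10.2.1 and 10.2.2 then plan a Fisher's exact test: "Toxicity will be collected and evaluated according to the NCI CTC toxicity scale (v4.0) and compared between the vaccinated and control groups".

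**What is measured.** Section 9.3 lists, at each visit, "CK test (HLA A2 positive patients only"), and restricts urine analysis in the same way. The HLA A2 negative schedule nevertheless includes urine testing for proteinuria. The ECG is a vaccinated-only item, and so are the autoimmune profiles after baseline. Visits 2 and 5 are not done in controls.

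**The concern.** An SAE window tied to the last dose suits a trial in which follow-up ends soon after treatment. Here follow-up outlasts treatment by about a year even in completers, and by far more in patients stopped early. Patients stopped for toxicity are those of most safety interest, and they leave the window soonest.

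The risks the protocol itself names are not all immediate: SLE-like autoimmunity (7.1.6), and cytopenia and renal or cardiac immune toxicity (7.1.8). The trial-level stopping discussion (4.5, 12.1) is triggered by life-threatening vaccine-related toxicity in more than one patient, so it depends on such events reaching the trials unit promptly.

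The second issue is separate. Section 8.1 counts an abnormal laboratory finding as an adverse event. If a test is scheduled in one group only, its abnormalities can appear by schedule in that group only. A formal test between groups then partly measures how hard each group was examined.

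**Working it through.** The plan states no figure on this point, so there is none to reproduce. The check is calendar arithmetic plus a comparison of sections.

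**1. Length of the window.** Inputs: 4 weeks after last dose (8.3.5); 36 months on study (9); dose times (5.2, 9.3). Formulas: window end = month of last dose + 28/30.4375 = month of last dose + 0.92; time outside = 36 − window end. Consent and week 0 are treated as the same origin, and visit tolerances are ignored.

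| Last dose | Window ends (month) | Outside window (months) | Share of 36 |
|---|---|---|---|
| Dose 12, month 23 | 23.92 | 12.08 | 33.6% |
| 24-month maximum in 5.2 | 24.92 | 11.08 | 30.8% |
| Dose 6, week 20 (140/30.4375 = month 4.60) | 5.52 | 30.48 | 84.7% |
| Dose 1, week 0 | 0.92 | 35.08 | 97.4% |
| Control, no dose | undefined | undefined | undefined |

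For a completer, the visits at months 27, 30, 33 and 36 fall after the window.

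Early exit may be common in AML. Section 1.1.3 anticipates relapse in 60–75% within 2 years, and progression ends vaccination (4.4). If the vaccine left that risk unchanged, this would be 0.60 × 39 = 23 to 0.75 × 39 = 29 of the 39 vaccinated AML patients. Fewer would remain under observation, because some will die.

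**2. Do other rules cover a new serious event in, say, month 30 of a patient still attending?**

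- The related-event clause in 8.3.5 starts when participation has been discontinued or has ended. This patient's has not.
- Follow-up of unresolved events concerns events already known.
- Section 8.3 says all adverse events should be reported, but gives no deadline. The one-month deadline in 8.3.2 is headed for non-serious events.
- Section 8.3.3 gives sites 24 hours for fatal or life-threatening SAEs and SUSARs, and 8.3.4 gives 24 hours for all SAE/SUSAR forms. Section 8.3.5 does not say whether either duty outlives the window.
- The trials unit's duty to notify SUSARs during the trial (8.3.4) depends on a site report.

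The event would therefore be collected as an adverse event. Whether it must be expedited is unclear, most of all when it is not judged a SUSAR.

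**3. Ascertainment by group** (schedules; 9.1, 9.3).

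| Item | Vaccinated | Control |
|---|---|---|
| Adverse-event visits, baseline to month 36 | 24 (visits 0–23) | 24 − 2 = 22 |
| CK | every visit | none |
| ECG at vaccination visits | 12 | none |
| Autoimmune profile after baseline | 4 (visits 7, 10, 16, 23) | none |
| Injection-site examination and pain assessment | yes | not applicable |
| FBC and biochemistry | 24 visits | 22 visits |
| Urinalysis | yes | no in 9.1/9.3; yes in the schedule |

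Blood counts and routine biochemistry are close to balanced. CK, ECG, autoimmune and injection-site findings are not.

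**The case against.** The strongest reply is that safety surveillance does not stop at month 24. Both schedules mark adverse events to month 36, unresolved events are followed, SUSARs during the trial are notified, and event listings are reviewed every 2 to 3 months (12.1). A serious, unexpected event suspected to be vaccine-related is a SUSAR. All of this stands. A reader might infer that no SAE rule exists after the window closes, and that goes too far. What lapses is the general duty to report SAEs whatever their cause. Nor does routine collection of adverse events to month 36 contradict an earlier end to expedited reporting, since the two are separate processes.

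A reader might also infer that the unequal windows bias the planned comparison, and compute SAE percentages over 24 against 36 months. The documents do not support this. The planned test uses CTCAE toxicity, which is collected in both groups to month 36, and not SAE forms. No text says that controls are counted for 36 months of SAE reports. Neither the size nor the direction of such a bias can be derived.

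On ascertainment, it is fair to say that the extra tests monitor vaccine and electroporation effects, that controls enter only where relevant, and that the choice of terms for the test may be left to an analysis plan not shown here. This softens the point but does not remove it. The protocol fixes both the unequal schedule and the between-group test, and the qualifier does not say which toxicities are comparable.

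**Conclusion.** The point holds in two parts.

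First, the general SAE requirement ends about 12 months before the end of study in a completer and up to about 35 months before it in a patient stopped after dose 1. It has no anchor for controls. This is a gap in the reporting text. It rests only on the stated dose times and follow-up, and assumes patients stay on study after vaccination stops, as Section 9 intends.

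Second, and independently, the Fisher's exact comparison of toxicity takes in findings sought by schedule in one group only. The likely direction is more CK, ECG and autoimmune abnormalities recorded in vaccinated patients. The size cannot be computed, because the protocol gives no background rates for these findings and does not state which terms enter the test. Cytopenia and routine biochemistry are little affected.

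The mismatch on urinalysis in controls is a plain inconsistency between 9.1/9.3 and the HLA A2 negative schedule. All three matters should be corrected. None bears on the primary endpoints.

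**What to change.** 1. In 8.3.5, state one SAE reporting period for both HLA groups, anchored to consent and study visits rather than to the last dose. At minimum it should cover SAEs possibly related to the study up to month 36, whether or not vaccination has stopped. Say explicitly how it fits with 8.3 and 8.3.4. Whether to report SAEs of any cause throughout is the sponsor's choice; if SAEs are ever tabulated by group, the same rule and period must apply to both.

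2. In 10.2.1 and 10.2.2, limit the vaccinated-versus-control toxicity test to events from visits and tests scheduled in both groups over the same period. Report CK, ECG, autoimmune and injection-site findings, and anything found at visits 2 and 5, descriptively for vaccinated patients. If the analysis plan already does this, a cross-reference is enough.

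3. Make 9.1, 9.3 and the HLA A2 negative schedule agree on urinalysis.

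The cost is a protocol amendment, a few more SAE forms and a narrower comparative test. The extra load is small: visits already run to month 36, and relapse and death from leukaemia are already exempt from SAE reporting (8.3.3).
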